Cover Page for ClinicalTrials.gov

Document: Study Protocol and Statistical Plan

Official Study Title: Racial inequities in end-of-life healthcare: how perceived discrimination affects communication and decision-making during serious illness

NCT Number: NCT04915079

Document Date: December 7, 2022

Research Protocol for PRISM pilot RCT

Final Draft: December 7, 2022

Goal:

Original Aim: Conduct a pilot randomized trial of 60 patients to test the feasibility, acceptability, and preliminary efficacy of a patient-centered intervention to cultivate resilience and improve patient-clinician communication and shared decision-making in seriously ill patients who have experienced healthcare discrimination. I will utilize a version of an established intervention to improve resilience and empower patients to effectively communicate with clinicians.

Hypothesis: This pilot RCT will establish feasibility and acceptability and show preliminary efficacy in improving resilience and quality of communication.

PRISM Pilot RCT Phases	
Pre-Study	
• IRB approval obtained• Study surveys developed
○ Enrollment○ 1-month○ 3-month• PRISM manual finalized• Provider script finalized• Patient interview script• Provider interview script• RedCap database created
Phase 1: Planning	
• Goal enrollment: 60 participants
○ 30 PRISM arm○ 30 usual care• Research question• Inclusion/Exclusion criteria
Phase 2: Conducting	
• Data extraction: EHR, survey results• Data synthesis: RedCap, DeDoose
Phase 3: Reporting	
• Dissemination of results

1. Getting Started:

- Phase 1 should be completed

2. Selecting Cases:

- Patients will be screened in the EHR. Eligible patients will be
 - Black
 - Diagnosed with serious illness with median expected survival of two years or less
 - English-speaking
 - Age 18 years and older
 - No cognitive impairment.

3. Instruments:

- Participants will complete three surveys upon
 - A) enrollment
 - B) 1-month post-randomization
 - and C) 3-months post randomization
- They will receive \$20 gift cards with each survey
- At enrollment, they will complete:
 - Demographic information
 - DMS
 - MHCS
 - GBMM
 - CD-RISC
 - HADS
- PRISM participants will also complete a post-PRISM qualitative interview
- At 1-month and 3-months post-enrollment, participants will complete
 - CD-RISC
 - HADS

4. Entering the Field

- Patients will continue to be enrolled in the ongoing cohort, but will also be approached regarding participating in a pilot RCT.
- Study goals will be explained and consent obtained prior to enrollment in the RCT.
- Note that patients will need to be consented for both the cohort and the RCT each.
- Participants will be randomized 1:1 to either PRISM or usual care using a random number generator (range 1-100; odd=usual care; even=PRISM)
- PRISM RCT participants will be tracked in RedCap and will include:
 - Enrollment survey results
 - 1-month survey results
 - 3-month survey results
 - Contact information including address, phone number, and email
- Provide patients with dates of follow up surveys upon enrollment.

- Participants will receive reminder phone-calls and emails 1 week before each survey, and in-person check-ins if they are readmitted or have an upcoming clinic visit during a 2-week window around each survey.
- If surveys are not completed within 1 week, participants will receive a phone call and email to remind them and assess willingness to continue participation

5. Analyzing Data

- Primary outcome: Differences in CD-RISC scores in PRISM vs usual care group at 1- and 3- months post randomization
- Statistical Analysis: My primary outcome is resilience, measured by the CD-RISC. I will use the intention-to-treat principle for analysis and use linear regression to evaluate differences in mean resilience at 3 months between the two study arms. I will adjust for baseline CD-RISC scores since I anticipate resilience at randomization and 3 months later will be highly correlated. For secondary analyses, I will adjust for age, sex, race/ethnicity, marital status, and diagnosis. I will also jointly model resilience scores at all time points (randomization, and 1- and 3-months) using a mixed model approach to evaluate trends in resilience scores. This approach accommodates missing outcomes, assuming data are missing at random. I will use a similar approach for my secondary, continuous outcomes. I will use logistic regression for dichotomous outcomes.
- Power: To calculate sample size, I used the difference in mean change in resilience scores, due to anticipated correlations between scores over time (Table 4). The standard deviation of change in the 10-item CD-RISC scores over 6 months (4.2 points) was available from a prior trial.⁵⁵ With 30 participants per arm, I will have 80% power at a 0.05 two-sided significance level to detect a mean change in CD-RISC scores over 3 months of 3 points (Table 4). I expect power to be similar or greater after adjusting for baseline resilience scores. I anticipate $\geq 70\%$ complete data and will randomize 43 patients per arm to achieve 30 patients with complete data. With 80% completion, I will have 80% power to detect a change of 2.8 points at the same significance level.
- Anticipated papers:
 - PRISM RCT
 - Clinician interviews
 - Patient interviews
 - Experience/feedback on racial healing/medical racism session?

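### Enrolment is set at 60 in the Aim and Phase 1 but at 86 in the power paragraph; at 60, the stated 80% power for 3 points is not reached under the plan's own completion assumption

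*Combined protocol and SAP*

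**What the plan says.** Two places give the target as 60. The Original Aim, under Goal, is to "Conduct a pilot randomized trial of 60 patients to test the feasibility, acceptability, and preliminary efficacy". The PRISM Pilot RCT Phases table, under Phase 1: Planning, has "Goal enrollment: 60 participants", split 30 to PRISM and 30 to usual care.

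The Power item of Section 5 (Analyzing Data) gives another number. It starts from the analysed sample: "With 30 participants per arm, I will have 80% power at a 0.05 two-sided significance level". The effect in question is 3 points on the CD-RISC. It then allows for incomplete data, expecting at least 70% to be complete, and says that the investigator "will randomize 43 patients per arm to achieve 30 patients with complete data". That is 86 patients. A second scenario follows: "With 80% completion, I will have 80% power to detect a change of 2.8 points at the same significance level".

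**The concern.** The number randomized cannot be both 60 and 86. The Phase 1 table calls 60 an enrolment goal, so it cannot be read as the number of completers, and the power paragraph itself separates those randomized (43 per arm) from those with complete data (30 per arm).

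Staff working from Phase 1 would stop at 60. A reader of Section 5 would credit the trial with 80% power for 3 points on the CD-RISC, the primary outcome. If the trial stopped at 60 and found no difference, that result could be given more weight against a 3-point effect than the data support.

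**Working it through.** **Inputs.** From Section 5, Power: SD of change 4.2 points; difference 3 points; two-sided alpha 0.05; power 80%; completion at least 70%, with an 80% scenario. From Section 4: 1:1 allocation. From the Aim and Phase 1: 60 enrolled, 30 per arm. Table 4, cited in the power paragraph, is not in the available text and was not checked.

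**Step 1: reproduce the plan's own figures (normal approximation).**
- Required n per arm = 2 × 4.2² × (1.960 + 0.842)² / 3² = 30.8, so 31; the plan says 30. Power at 30 per arm is 79.0% (77.6% by the noncentral t).
- Inflation: 30 / 0.70 = 42.9, so 43 per arm and 86 in total.
- At 80% completion: 43 × 0.80 = 34.4 per arm. Detectable difference = (1.960 + 0.842) × 4.2 × √(2/34.4) = 2.84, matching the stated 2.8.

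The power paragraph is therefore consistent with itself, within rounding, and it is built on 86 randomized.

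**Step 2: apply the same assumptions to 60 randomized.** Completers per arm are 30 × 0.70 = 21 or 30 × 0.80 = 24. With standard error 4.2 × √(2/n):

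| Completion | n per arm | Power for 3 points, t (normal) | Difference at 80% power, t (normal) |
|---|---|---|---|
| 70% | 21 | 61.7% (63.9%) | 3.72 (3.63) |
| 80% | 24 | 67.8% (69.7%) | 3.47 (3.40) |
| 90% | 27 | 73% (74.7%) | not needed here |
| 100% | 30 | 77.6% (79.0%) | 3.09 (3.04) |

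Only full completion brings 60 randomized close to the stated 80%. The 2.8-point figure does not arise from 60: at 80% completion the like-for-like normal value is 3.40.

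**Step 3: credit the baseline adjustment in the primary analysis.** The plan gives no correlation between baseline and 3-month scores, so a range is assumed. With equal variances at both times and the SD of change held at 4.2, the residual SD is 4.2 × √((1 + ρ)/2).

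| Assumed ρ | Residual SD | Power for 3 points at 21 per arm, t (normal) |
|---|---|---|
| 0.5 | 3.64 | 74% (76%) |
| 0.6 | 3.76 | 71% (74%) |
| 0.7 | 3.87 | 69% (71%) |
| 0.8 | 3.98 | 66% (68%) |

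At 24 per arm the t-based range over ρ = 0.8 to 0.5 is 72% to 80%. At 21 per arm, 80% power needs ρ of about 0.3 (t) or 0.37 (normal) or lower. The Statistical Analysis item expects the two scores to be strongly correlated, which points the other way.

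**Step 4: size of the discrepancy.** 86 − 60 = 26 patients, and 26 / 60 = 43%.

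**The case against.** The best defence is that 60 is carried-over text. The Aim is labelled as original, and 60 is exactly twice the completer target of 30, so the analysed number may have been copied into the enrolment field. That may well be how the conflict arose, but it does not remove it: the Phase 1 table repeats 60 as enrolment without that label, and no revised aim is given.

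Second, the power paragraph never claims 80% power for 60 randomized. This is true, and the loss is conditional on stopping at 60. But 60 is the enrolment goal that the plan states.

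Third, the lowest power figures are a floor. Completion is expected to be at least 70%, the primary analysis adjusts for baseline, and the plan's own figures match the normal approximation rather than the t-test. All of this stands. Changing the method moves power by about 2 percentage points and the detectable difference by about 0.1 point. The most favourable combination examined, 80% completion with a correlation of 0.5, does reach about 80% power. A mixed model using partial follow-up might also recover a little. At the completion rate used to set the sample size, no correlation from 0.5 to 0.8 restores 80%.

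Fourth, this is a pilot, and 60 patients may be enough for feasibility and acceptability. That is a fair reason to keep 60. It is not a reason to leave beside it a power claim that belongs to 86.

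**Conclusion.** The contradiction is real, and the plan is wrong as written. The power paragraph is sound for 86 randomized; the shortfall comes from pairing it with an enrolment goal of 60.

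At 60 and 70% completion, the chance of missing a true 3-point difference is about 38% by the t-test (36% by the normal approximation), against the 20% implied. These figures take the plan's SD of change, which was observed over 6 months in a prior trial, as applying at 3 months. They also assume equal completion in the two arms. The baseline-adjusted figures rest further on the assumed correlations and equal variances. Confidence in the finding is high, because the conflict can be read directly from the text and the plan's own numbers reproduce.

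**What to change.** State one number randomized in the Aim, the Phase 1 table and the power paragraph. The choice is the sponsor's.

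- **If 86 governs:** change the Aim and Phase 1 to 86 randomized (43 per arm), expecting about 60 with complete data. The power paragraph can stay.
- **If 60 governs:** remove the 43 per arm and restate power for the expected completers. At 70% completion this is about 21 per arm, 62% power for 3 points, and 80% power for 3.7 points. At 80% completion it is about 24 per arm, 68% power for 3 points, and 80% power for 3.5 points. If credit is taken for baseline adjustment, give the assumed correlation.

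In either case, name the 3 points as a between-arm difference in mean change where the figure is stated, and use one calculation method throughout. If the t-test is chosen, 30 per arm gives 3.1 points and 34 per arm gives 2.9, in place of 3 and 2.8.

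The edit itself is to protocol wording only. Keeping 60 costs a less favourable stated detectable difference; adopting 86 commits the trial to recruiting 26 more patients than the Phase 1 goal.
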